Data to be collected will consist of maternal age and ethnicity, gravida/para, gestational age, height, weight, estimated fetal weight, reason for induction, date and time of device placement, date and time of delivery, mode of delivery, Bishop score at eligibility assessment, Bishop score prior to dilator insertion, Bishop score after removal or expulsion of dilator, date and time of rupture of membranes, date and time of device expulsion/removal, hospital length of stay, other intrapartum and obstetrical interventions, complications in device placement and cervical ripening, during labor and delivery including but not limited to meconium, infections, hemorrhage, fetal decelerations and subject satisfaction. We will also collect the amount of analgesics subjects received during device placement, cervical ripening and induction time (includes acetaminophen or intravenous medications or regional anesthesia). Data will be abstracted from the medical records as well as from direct interview. We will also collect basic neonatal data including birth weight, Apgar scores, rate of admission to neonatal intensive care unit, infections, and other neonatal complications. The data collected will not be used for clinical diagnosis or treatment purposes. Additional economic data to be collected includes the following admission direct costs or charges from the following services/departments: Blood Bank Transfusion Operations, Chemistry Division, Hematopathology Division, JSH Labor & Delivery unit, Materials Management, Microbiology Division, Mother Baby Unit, Pharmacy, Respiratory Care Services, Surgical Operating Suite.

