### **5.4. Pre-Induction**

#### **5.4.1. Group Assigned to Outpatient Cervical Ripening**

After Dilapan-S® placement, subject will be monitored for at least 30 minutes. If no contraindications, such as tachysystole, active vaginal bleeding, rupture of membranes or nonreassuring fetal testing (defined as minimal or absent variability, abnormal baseline, or presence of decelerations) evidence of labor, or other serious medical conditions deemed by the clinical staff or the attending physician to preclude outpatient cervical ripening develop after insertion, the subjects will be randomized. After randomization subject will record the pain she experienced during insertion in the patient's survey (see Appendix 3). Those subjects randomized to outpatient ripening will be given the option to either stay in a hotel or, if they are able to reach the hospital within 60 minutes, return home. The cost for the hotel will be covered by the study budget. Subjects at CUMC will solely be given the option to stay at home. Subjects will be allowed to ambulate, shower and perform regular activity during that period. "Nothing per vagina" will be allowed (incl. intercourse, tampons etc.). Subjects will also be instructed to return to L&D unit 12 hours after insertion, or earlier if any excessive bleeding, rupture of membranes, pain or other concerns (contractions, decreased fetal movement) develop before the 12 hours. Special leaflet (Appendix 2) will be provided to subjects leaving the hospital, with detailed instruction, emergency contacts to appropriate study/clinical staff and space to document of oral medication taken for pain relief (acetaminophen). Subject will also document the date and time of membrane rupture if applicable.

Reasons for examining or removing dilators earlier include but are not limited to:

- 1) Spontaneous onset of labor  
(defined as regular, firm, uterine contractions with an effaced cervix >80% and a cervical dilatation > 3 cm)
- 2) Other than category I fetal heart rate tracing  
(category I includes all: Baseline rate: 110–160 beats per minute, baseline FHR variability: moderate, absent late or variable decelerations, Early decelerations: present or absent and accelerations: present or absent)
- 3) Spontaneous rupture of membranes or need for amniotomy
- 4) Spontaneous expulsion of Dilapan-S® rods
- 5) Subject removed the rods herself

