After the designated 12 hours' time or earlier, if indicated, subjects are to return and to be admitted to L&D unit for standard protocol of labor induction. If the cervix remains unfavorable after extraction or spontaneous expulsion of the dilators (< 3cm and at most 60% effaced), additional mechanical or pharmacological cervical ripening may be provided at the provider's discretion. The agent/type will be recorded into the data sheet.

If subject does not return in the designated time and date as instructed (12 hours window), all attempts will be made to contact the subject by phone or supporting contact person. Subject will also be instructed that if she presents to another hospital, she needs to inform the clinical staff seeing her that she is participating in a trial and that Dilapan-S® was placed for cervical ripening, and to present the study card. We will also do our best to obtain our primary outcome through release of records.

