### **VISIT #2**

#### **5.5. Labor Induction and Labor**

Management of the subject after the initial 12 hours of pre-induction or following the earlier removal or spontaneous expulsion of the dilator will be the same for both groups and at the discretion of the clinical team. Additional ripening (mechanical or prostaglandins) and/or oxytocin may or may not be needed. If needed, duration, type and dose of additional ripening agents and oxytocin will be documented.

Routine intrapartum care will be provided and relevant data collected by the subject's managing obstetrical team.

Trained and experienced research staff will be responsible for all research data abstraction. The PI and collaborators will review and validate the outcomes. If there is uncertainty, a second investigator will review the chart, discuss with the other investigators as needed, and make a final determination regarding the outcome.

Subjective assessment data will be collected, using adequate validated tools either after Dilapan-S® extraction or any time prior labor or post-partum (Appendix 3) at the time point best suitable for both the subject and the study team.

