### **6.2. Secondary Outcomes**

- Rate of vaginal deliveries (%)
- Rate of vaginal deliveries within 24 hours since admission to hospital (%)
- Rate of vaginal deliveries within 36 hours since admission to hospital (%)
- Time from hospital admission to reach active stage of labor defined as  $\geq 6$  cm (mins)
- Time from device placement to reach active stage of labor defined as  $\geq 6$  cm (mins)

- Change in Bishop score from insertion to extraction of device
- Change in cervical dilation after Dilapan-S®
- Rate of spontaneous vaginal deliveries after one round of cervical ripening (%) (no additional medical or mechanical interventions)
- Rate of operative vaginal deliveries (%)
- Rate of caesarean deliveries (%)
- Rate of artificial rupture of membranes (AROM) (%)
- Rate of epidural analgesia (%)
- Total duration of Dilapan-S® application (insertion to removal/extraction) (mins)
- Device placement to delivery interval (mins)
- Induction (Oxytocin/Prostaglandin initiation) to delivery interval (mins)
- Analgesia used during device placement (%), cervical ripening (%) and labor induction (%)
- Rate of adverse neonatal outcomes (composite and individual) –Apgar score <7 at 1-5-10 minutes, Cord arterial pH <7.1, neonatal ICU admission (%)
- Occurrence of maternal and neonatal complications within 2 weeks after delivery (%)
- Total duration of maternal hospital stay (hours)
- Subject reported clinical outcomes (sleep, rest, pain, activities of daily living, etc.) (Appendix 3)
- Subject reported satisfaction with Dilapan-S® treatment (Appendix 3)
- Medicaid charges for each hospitalized subject in both arms

*(Blood Bank Transfusion Operations, Chemistry Division, Hematopathology Division, JSH Labor & Delivery unit, Materials Management, Microbiology Division, Mother Baby Unit, Pharmacy, Respiratory Care Services, Surgical Operating Suite)*

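### The drug-start-to-delivery interval begins at a point set by discretionary care after randomisation and is missing for women given neither drug, so testing it between arms is not a comparison of all randomised women

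*Combined protocol and SAP*

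**What the plan says.** Section 6.2 lists the outcome as "Induction (Oxytocin/Prostaglandin initiation) to delivery interval (mins"). The clock therefore needs one of two drugs to be given.

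Section 5.4.1 says that, if the cervix is still unfavourable once the rods are out, "additional mechanical or pharmacological cervical ripening may be provided at the provider's discretion". Section 5.4.2 applies the same management to inpatients. Section 5.5 adds that "Additional ripening (mechanical or prostaglandins) and/or oxytocin may or may not be needed".

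The plan expects some women to receive neither drug. "Spontaneous onset of labor" is among the reasons in section 5.4.1 for examining or removing the rods early. Section 6.2 also has an outcome for spontaneous vaginal delivery after a single round with "no additional medical or mechanical interventions".

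Two statements in section 5.5 point the other way. Management after ripening "will be the same for both groups and at the discretion of the clinical team", and "If needed, duration, type and dose of additional ripening agents and oxytocin will be documented".

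For analysis, section 13.3 gives general rules: a t-test or Wilcoxon-Mann-Whitney test for continuous variables, and Kaplan-Meier with a log-rank test by ITT for time-to-event outcomes. Section 13.1 defines ITT as randomised women whose primary outcome was obtained. Neither section says what to do with a mechanical second round or with a woman who has no start time. Section 13 defers further detail to a SAP to be approved before database lock, and the documents supplied contain no such rule.

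**The concern.** Two features of the definition depend on care given after randomisation.

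- **The start.** Two women with the same course from rod removal to delivery can have different values, because a prostaglandin round falls inside the interval and a mechanical round can fall outside it.
- **Who is counted.** A woman who labours without either drug has no interval. She cannot enter a t-test, nor be placed on a Kaplan-Meier curve, so an analysis called ITT would be run in a subset.

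Staff necessarily know whether a woman ripened at home or on the unit, and the choice of agent is theirs. If that choice, or the share needing no drug, differs between arms, the difference appears as one in labour duration and would be read as an effect of setting. The direction can also mislead: if fast labourers in one arm more often need no drug, they leave the comparison and that arm looks slower.

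**Working it through.** **Plan's own figure.** The documents give none for this interval. The only sample size is for the primary outcome (section 13.4: 54% v 37.8%, 85% power, two-sided 0.05). It reproduces as 169 per group with pooled variance and no continuity correction; 169/0.90 rounds up to 188, so 376 in total. Nothing below changes it.

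**Step 1: when the clock starts.** Reading sections 5.4.1, 5.5 and 6.2 together:

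| Course after the rods are out | Clock starts | Second round counted? |
|---|---|---|
| No second round, oxytocin given | at oxytocin | not applicable |
| Second round with prostaglandin | at prostaglandin | yes |
| Mechanical second round, drug afterwards | at the later drug | no |
| Mechanical second round with oxytocin alongside | during the round | in part |
| Neither drug at any point | never | no value |

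For a round of length L followed by time T to delivery, the second row gives L + T and the third gives T.

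**Step 2: shift from agent mix.** If true time to delivery is the same in both arms and rounds are sequential, the spurious mean difference is

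share having a second round × difference between arms in mechanical share × L.

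All inputs are assumptions. The only related figure in the documents is the statement in section 1 that mechanical ripening can take up to 12 hours; it describes a first dilator and is an upper limit.

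- 20% second round, 70% v 30% mechanical, 12 h: 0.20 × 0.40 × 12 = 0.96 h
- 10% second round, otherwise the same: 0.10 × 0.40 × 12 = 0.48 h
- 30% second round, otherwise the same: 0.30 × 0.40 × 12 = 1.44 h
- 20% second round, 50% v 40% mechanical, 6 h: 0.20 × 0.10 × 6 = 0.12 h

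The illustrative range is thus about 0.1 to 1.4 h. If some women have no value, the result is divided by the share who have one.

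**Step 3: effect on the test.** A simulation used 169 per arm, 4,000 runs, a Welch t-test and the same distribution of time to delivery in both arms. The assumptions, none from the documents, were: removal to delivery mean 960 min, SD 480; 40% have a second round, which adds 360 min with either agent; 10% receive neither drug unless varied. When the neither-drug share was varied, these were mainly faster labourers.

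| Scenario (arm A v arm B) | Spurious difference | Rejections at 5% |
|---|---|---|
| Same agent mix and drug receipt | 0 min | 4.9% |
| Prostaglandin share 40% v 60% | 34 min | 8.9% |
| Prostaglandin share 30% v 70% | 64 min | 18.8% |
| Prostaglandin share 20% v 80% | 97 min | 40% |
| Neither drug 5% v 15% | 49 min | 14.5% |
| Neither drug 5% v 25% | 92 min | 34% |
| Prostaglandin 30% v 70% and neither drug 5% v 20% | 139 min | 67% |

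Arithmetic check on the third row: 0.40 × 0.40 × 360/0.90 = 64 min. With a start common to all women and everyone included, rejections were 4.8% to 5.5% in every scenario.

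**Step 4: is there a sound alternative in the plan?** Section 6.2 also lists the interval from device placement to delivery. Sections 5.1 and 5.3 put placement before randomisation, so every randomised woman has that start, and any second round counts whatever its type.

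**The case against.** The strongest reply is that the bias is conditional. Section 5.5 says that management after ripening is the same for both groups, and nothing in the documents shows agent choice or drug receipt differing by arm. When they do not differ, the test keeps its level (4.9% in the simulation). This stands: the documents establish a gap in the definition, not a bias.

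Four stronger readings are tempting, and the documents do not support them.

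- *Site habits would bias the result.* Sections 3 and 5.3 give UTMB and CUMC separate randomisation sequences, so a site's preference falls on both arms in expectation.
- *A woman's value can move by about 12 h.* That takes section 1's upper limit for a first dilator as the length of a second round, and assumes the drug always follows the round. Section 5.5 does not rule out oxytocin during it.
- *The size is known.* Second-round share, agent split and round length are all assumed, and the result is proportional to each.
- *Removal-to-delivery should replace the outcome.* Section 3 does list "date and time of device expulsion/removal" among the data. But removal also comes after randomisation, and outpatients must first travel back. Section 5.4.1 has women at home note oral pain medication and membrane rupture; it does not mention expulsion time. Using the first examination when that time is unknown would mainly start outpatients' clocks late and shorten their intervals.

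It can also be said that this is one of 22 secondary outcomes, that agents are recorded, that placement-to-delivery is already planned, and that handling rules belong in the SAP. All true, and they limit the weight of the point. They do not remove it: as written, section 13.3 would still test this interval and report it as a comparison of the randomised arms.

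**Conclusion.** The concern holds in a limited form. The interval's start depends on discretionary care after randomisation, women given neither drug have no value, and the documents supplied have no rule for either case. A between-arm test is therefore not a comparison of all randomised women.

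Whether it would mislead depends on agent mix or drug receipt differing by arm, which the documents neither show nor exclude. The size is unknown. The assumed inputs in step 2 give about 0.1 to 1.4 h from agent mix alone; more extreme mixes, or selective loss of fast labourers as well, gave more in the simulation. A reader should not infer that the arms will differ spuriously, or that the primary outcome or the sample size of 376 is in doubt.

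**What to change.** In section 6.2 and the SAP, before database lock:

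1. Make the drug-start-to-delivery interval descriptive, with no between-arm test. State which event starts the clock when a second round is given.
2. Report by arm the number of women with no value and the type of second ripening. Sections 5.4.1 and 5.5 already have agent type recorded.
3. Name the placement-to-delivery interval as the randomised time-to-delivery comparison.
4. Optionally add removal or expulsion to delivery as a supportive descriptive interval, with the number of unknown expulsion times by arm. It should not serve as a randomised comparison.

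The cost is a few lines of text and the loss of one secondary p-value. Care, data collection and sample size do not change.

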## 7. Inclusion and Exclusion Criteria

### 7.1. Criteria for Inclusion of Subjects:

Subjects must meet all of the inclusion criteria in order to be eligible to participate in the study.

Inclusion criteria are:

1. Pregnant woman whose plan of care is induction of labor
2. Maternal age between 18 and 45 years
3. Understanding and capable to sign informed consent
4. Singleton pregnancy
5. Gestational age  $\geq 37^{0/7}$  weeks  
(based on a sure last menstrual period or a first trimester dating ultrasound)
6. Live fetus in cephalic presentation
7. Intact membranes
8. Pelvic exam (sterile vaginal exam) of less than or equal to 3cm and at most 60% effaced

### 7.2. Criteria for Exclusion of Subjects

Subjects meeting any of the exclusion criteria at baseline will be excluded from study participation.

Exclusion Criteria are:

1. Active labor
2. Active genital herpes
3. Chorioamnionitis
4. Transfundal uterine or cervical surgery
5. Previous cesarean delivery

6. Non-reassuring fetal status
7. Need for continuous maternal or fetal monitoring during ripening
8. Contraindication for vaginal delivery
9. Active vaginal bleeding
10. Abnormal placental location or adherence (placenta previa or unresolved low lying placenta)
11. Estimated fetal weight  $> 5000$  g (non diabetic) or  $> 4500$  g (diabetic)
12. Intrauterine growth restriction (estimated fetal weight  $< 10$  percentile)
13. Oligohydramnios (amniotic fluid index  $< 5$ cm or deep vertical pocket of  $< 2$  cm)
14. Fetal anomaly
15. Need for inpatient care (e.g. hypertension, insulin-dependent diabetes)
16. Poor or no access to a telephone and cannot be placed in the hotel
17. Absence of support person ( no adult accompanying the subject during outpatient cervical ripening period)

## **8. Sources of Research Data**

Medical chart/records, charges for Medicaid services report forms and direct cost reports will be used as source for data collection.

## 9. Potential Risks

### 9.1. Randomization risk

Since the location of pre-induction management will be randomized, it is possible that the subject may be in a group with higher adverse outcomes.

### 9.2. Loss of Confidentiality

Any time information is collected, there is a potential risk for loss of confidentiality. Every effort will be made to keep subject's information confidential; however, this cannot be guaranteed.

### 9.3. Risks associated with mechanical dilator

- Vaginal bleeding during/after device insertion
- Subjective pain felt during insertion
- Vaso-vagal reaction from manipulation of the cervix
- Contamination of the device during insertion
- Allergic reaction from hypersensitivity to the components
- Rupture of membranes
- Uterine tachysystole (> 5 contractions in 10 mins averaged over 30)
- Cervical trauma during insertion or extraction.
- Retraction of the device into the uterine cavity
- Entrapment of the device
- Fragmentation of the device

## 10. Subject Safety and Data Monitoring

### 10.1. Safety reporting

#### Scope

In relation to Dilapan-S®, the Clinical Trial is a post-market clinical follow-up study (PMCF) conducted using CE marked device ("Conformité Européenne") within its intended use. The provisions of Directive 93/42/EEC concerning information and notification of incidents occurring following placing devices on the market are fully applicable. Medical Device Reporting regulation (21 CFR 803) will be followed to report certain device related adverse events and product problems to the FDA.

The Investigator shall ensure that Sponsor will be informed about any adverse events (AEs) that would be related to study device according to the definitions given below. Complaints about any product problem are within the scope of obligatory notification too, including product defects, malfunctions or user errors.

AEs not related to the study device are not to be reported to sponsor. Borderline events should be handled conservatively and the sponsor should be notified in case of any doubt.

#### Definitions

**Adverse Event (AE)** is any untoward medical occurrence in a subject and that does not necessarily have a causal relationship to the study device and surgical procedure.

**Serious Adverse Event (SAE)** is any AE that:

- Results in death.
- Is life-threatening.
- Leads to hospitalization or prolongation of hospitalization.
- Causes disability and/or permanent impairment of a body function or structure.

- Requires medical or surgical intervention to prevent permanent impairment of a body function or permanent damage to a body structure.
- Leads to fetal demise, a congenital abnormality, or birth defect.

**Product Problem** includes:

- Inadequacy of a medical device with respect to its identity, quality, durability, reliability, safety or performance. It also includes inadequate labelling.
- Malfunction: failure of an investigational medical device to perform in accordance with its intended purpose when used in accordance with the instructions for use or Clinical Investigation Plan.
- User error: act or omission of an act that results in a different medical device response than intended by the manufacturer or expected by the user.

**Evaluation of an AE**

When evaluating AEs, the Investigator must determine:

- if the event is serious. Seriousness criteria are based on definition of an SAE (above).
- if the event is related to the study device. The following rules are to be applied:
  - a) Not Related: AE which are clearly and incontrovertibly due to causes other than the study device (e.g., concomitant disease).
  - b) Related: AE which are felt with a reasonable degree of certainty to be related to the study device.
  - c) Unknown: AEs for which a connection with the study device cannot be ruled-out with certainty, or not enough information is available to assess the relationship.

**Reporting**

The collection of AEs begins at the time the subject is enrolled into the study (eligible subject with signed informed consent).

Reporting will be done in written via the attached Safety Report Form (Appendix 4).

The Investigator is obligated to send the applicable report to the Sponsor within 24 hours of becoming aware of the event to ensure the safety of all participants in the study and to meet regulatory reporting requirements.

Subsequent reporting to the IRB and the corresponding regulatory authorities will be organized by the Sponsor and in accordance with all applicable legal requirements of the concerned country.

